4.2. Exclusion criteria

1. Patients who received prior anticancer treatment within 14 days (or 5 times the half-life time, whichever is shorter) or any investigational agent within 28 days prior to the first dose of study drugs.
2. Patients who have undergone surgical treatment and radiotherapy within 2 weeks before enrollment.
3. Patients with a history of prior treatment with Lenvatinib or any anti-PD-1, anti-PD-L1, or anti-PD-L2 agent.
4. Patients with hypertension that is difficult to control (systolic blood pressure ≥ 160 mmHg and diastolic blood pressure ≥ 90 mmHg) despite treatment with several hypotensive agents.
5. Patients with acute coronary syndrome (including myocardial infarction and unstable angina), and with a history of coronary angioplasty or stent placement performed within 6 months before enrollment.
6. Patients with symptomatic brain metastasis.
7. Patients with a history of New York Heart Association congestive heart failure of grade II or above, unstable angina, myocardial infarction within the past 6 months, or serious cardiac arrhythmia associated with significant cardiovascular impairment within the past 6 months
8. Patients have an active malignancy (except for definitively treated melanoma in-situ, basal or squamous cell carcinoma of the skin, or carcinoma in-situ of the cervix) within the past 24 months
9. Patients have severe (hospitalization required) complications (intestinal palsy, intestinal obstruction, pulmonary fibrosis, diabetes difficult to control, heart failure, myocardial infarction, unstable angina, renal failure, liver failure, mental disease, cerebrovascular disease etc).
10. Patients with a history of a gastrointestinal perforation and /or gastrointestinal fistula within 6 months before enrollment.
11. Patients with active hepatitis.
12. Patients with a history of human immunodeficiency virus (HIV).

13. Patients with active symptoms or signs of interstitial lung disease.
14. Patients with concurrent autoimmune disease, or a history of chronic or recurrent autoimmune disease
15. Patients who require systemic corticosteroids (excluding temporary usage for tests, prophylactic administration for allergic reactions, or to alleviate swelling associated with radiotherapy) or immunosuppressants, or who have received such a therapy <14 days before enrollment.
16. Patients have a history of (non-infectious) pneumonitis that required steroids or have current pneumonitis
17. Patients who are administered live vaccines <30 days before the initiation of treatment with the investigational drug.
18. Patients have serious non-healing wound, ulcer, or bone fracture.
19. Females who are pregnant or breastfeeding
20. Patients have no intention to comply with the protocol or cannot comply.
21. Patients were judged unsuitable as subject of this trial by investigator.

5. Registration/allocation

After confirming that target subjects satisfy all the eligibility criteria, and they are not corresponding to any one of the exclusion criteria, register them by the Web registration system.

5.2. Precautions for registration

- 1) Registration after start of the protocol treatment is not allowed without exception.
- 2) When confirmation of the contents of registration/eligibility confirmation sheet is inadequate, registration is not accepted until all the requirements are satisfied.
- 3) After confirmation of eligibility, a registration number is issued. Registration is completed upon issuance of the registration number.

- 4) When registered once, subject's registration is not cancelled (deletion from the database) except for cases of retraction of consent inclusive of rejection of the use of data for research. The initial registration information (registration number) is adopted in any cases of overlapped registration.
- 5) When erroneous registration/overlapped registration have been proved, this should be promptly informed.
- 6) When subjects are visiting other hospitals or departments continuously at the time of registration, inform the relevant investigator to the effect that the said subjects participate in this clinical trial.

6. TREATMENT PLAN AND CRITERIA FOR TREATMENT CHANGE

Treatment and treatment changes should be implemented as specified in this section unless otherwise threatening the patients' safety. When it is judged that compliance with the protocol may cause medical hazards, the principal investigator/subinvestigator (hereinafter referred to as the investigator) should change the treatment in accordance with the medical judgment.

6.1. Protocol Treatment

In the present trial, the protocol treatment will consist of the investigational drug, Lenvatinib, used in combination with Pembrolizumab. However, in the event that the termination criteria are satisfied for one of these drugs, the trial investigator can consider continuing the treatment protocol with either Lenvatinib or Pembrolizumab monotherapy upon deliberation with the trial coordinating committee. Each patients will undergo study treatment on an inpatient or outpatient basis.

The treatment protocol will commence within 14 days of enrollment, including the day of enrollment. Furthermore, in the event that administration of the investigational drug cannot be initiated within 14 days of enrollment (including the day of enrollment), the trial coordinating committee is to be contacted to examine how the patient should be handled.

The following terms are used in this protocol:

- Discontinuation: Investigational drug administration is not resumed.
- Treatment interruption: The protocol treatment is moved on to the next dosing schedule without administration of one or more doses of the investigational drug.
- Washout period: A period during which no investigational drug is given

6.1. 1 Study Treatment

- 1) Lenvatinib will be administered with water orally once a day (with or without food) in 21-day cycles at approximately the same time each day. On Day 1 of each cycle, in case concomitantly administered, it will be administered approximately within 1 hour after completion of pembrolizumab administration. Pembrolizumab will be administered as a dose of 200 mg as a 30-minute IV infusion, Q3W (25 minutes to 40 minutes are acceptable).
- 2) The initial dose of Lenvatinib will be 20 mg per day.
- 3) Continue administration until it will fall into "6.2.1. Discontinuation Criteria for the Protocol Treatment".

6.2. Discontinuation Criteria for the Protocol Treatment

6.2.1. Discontinuation Criteria for the Protocol Treatment

When the participating patients met any of the following criteria, the protocol treatment should be discontinued:

- 1) Progression of the primary disease (including evident progression based on diagnostic imaging and clinically clear progression)
- 2) Request for discontinuing the protocol treatment by the patient
- 3) Onset of protocol treatment-related Grade 4 non-hematotoxicity
(This is not applicable to transient abnormal laboratory values.)
- 4) Both lenvatinib and pembrolizumab are not administered for greater than 28 days.
- 5) Meeting the discontinuation criteria for the protocol treatment set forth in the Section “6.3. Criteria for Changes in the Protocol Treatment”
- 6) Recurrent Grade 2 pneumonitis
- 7) Pregnancy in the patients
- 8) Lost to follow-up
- 9) Death during the protocol treatment
- 10) Completed 35 treatments with Pembrolizumab
- 11) Treatment discontinuation after CR

Following at least eight cycles of pembrolizumab (approximately 6 months), when a subject is deemed to exhibit CR on the basis of diagnostic imaging, and receives at least two cycles of pembrolizumab after the initial determination of CR, termination of pembrolizumab can be considered upon consultation with the trial coordinating committee.

- 12) Other instances when the attending physician judges it necessary to terminate the trial (including when treatment with other anticancer drugs, surgery, or radiotherapy not stipulated in the protocol is needed for lesions that are subject to evaluation).

When, despite meeting the criteria for termination of the treatment protocol, there are clinical grounds that strongly suggest the efficacy of the treatment and there are reasons that justify the continuation of the protocol treatment, the decision shall be reconsidered with the trial coordinating committee on an individual basis according to the situation.

6.2.2. Data Collection and Follow-up of Patients after Discontinuation of the Protocol Treatment

When meeting the discontinuation criteria, the protocol treatment should be discontinued, its date, reason and clinical course should be recorded in the case report form (CRF), and

tests specified during the follow-up period should be performed. However, this is not applicable to the case where the investigator judges that the tests cannot be performed or are unnecessary in the light of ethics and the patients' safety and benefits.

6.3. Criteria for Dose Modifications for the Protocol Treatment

The treatment should be interrupted and resumed as instructed in this section. For patients who need to resume lenvatinib and pembrolizumab more than 28 days after the planned start day, the protocol treatment should be discontinued. However, even if lenvatinib or pembrolizumab therapy is discontinued, if another monotherapy can be resumed in accordance with this section, the protocol treatment may be resumed only monotherapy.

6.3.1. Criteria for Changes in Lenvatinib therapy

The safety profile of regorafenib has been established in the clinical trials. The dose adjustments for lenvatinib are according to the clinical trials conducted to date in table 6.3.1.

Table 6.3.1: Doses of Lenvatinib

Dose Level	Lenvatinib (mg,QD)
Initial dose	20 mg
Reduction 1	14 mg
Reduction 2	10 mg
Reduction 3	8 mg
Reduction 4	4 mg *

* Consult the coordinating committee for further dose reduction recommendations.

6.3.1.1 Dose modification of Lenvatinib

Lenvatinib dose reduction and interruption for subjects who experience lenvatinib and pembrolizumab combination therapy-related toxicity will be in accordance with the dose reduction instructions shown in the tables below for this study, respectively. Even if the following conditions are not met, it is possible to withdraw administration and reduce the dose at the discretion of the investigator. For management of hypertension, refer to the section 6.3.1.2. Once the dose has been reduced, it cannot be increased at a later date.

Table 6.3.1: Dose Modification of Lenvatinib

Lenvatinib Treatment-related Toxicity ^a ,	During Therapy	Adjusted Dose ^d

Grade 1, Tolerable Grade 2		
	Continue treatment	No change
Intolerable Grade 2^b and Grade 3^c		
First occurrence	Interrupt lenvatinib until resolved to tolerable Grade 2, or Grade 0-1	No change or Reduce lenvatinib by 1 dose level
Second occurrence (same toxicity or new toxicity)	Interrupt lenvatinib until resolved to tolerable Grade 2, or Grade 0-1	Reduce lenvatinib by 1 more dose level
Third occurrence (same toxicity or new toxicity)	Interrupt lenvatinib until resolved to tolerable Grade 2, or Grade 0-1	Reduce lenvatinib by 1 more dose level
Fourth occurrence (same toxicity or new toxicity)	Interrupt lenvatinib until resolved to tolerable Grade 2, or Grade 0-1	Reduce lenvatinib by 1 more dose level
Grade 4^c: Discontinue lenvatinib		

BMI = body mass index.
 
a: Excluding alopecia and asymptomatic laboratory abnormalities. Initiate optimal medical management for nausea, vomiting, hypothyroidism and/or diarrhea prior to any lenvatinib interruption or dose reduction.
 
b: Applicable only to Grade 2 toxicities judged by subject and/or physician to be intolerable.
 
c: Excluding laboratory abnormalities judged to be non-life-threatening, in which case manage as Grade 3. Asymptomatic laboratory value abnormalities will not be included.
 
d: Refer to the table 6.3.1.
		

6.3.1.2 Dose modification for hypertension

When hypertension develops during lenvatinib treatment, dose modification will be made at the discretion of the principal investigator (or subinvestigator) with reference to "Table 6.3.1.2: Dose modification for hypertension." Hypertensive subjects require careful observation and it is strongly recommended to administer suitable hypotensive treatment during lenvatinib treatment. The selection of hypotensive drug will be determined by the principal investigator (or subinvestigator) upon consideration of the treatment guidelines for

each institution participating in the trial.

Table 6.3.1.2 Dose modification for hypertension

NCI-CTCAE grade	Dose modification
Grade 2 Systolic blood pressure of 140–159 mmHg and/or diastolic blood pressure of 90–99 mmHg, or when the former is normal but diastolic blood pressure is increased > 20 mmHg and accompanied by symptoms.	Continue the dosing. If poorly controlled, consider a dose reduction. When accompanied by symptoms, withdraw treatment until the subject recovers from the symptoms, and diastolic blood pressure is restored to <90 mmHg. When resuming treatment, continue at the same dose level.
Grade 3 Elevated systolic blood pressure of \geq 160 mmHg and/or diastolic blood pressure of \geq 100 mmHg, or pharmacotherapy of two or more types, and greater intensive therapy than before is needed.	Withdraw treatment until the diastolic blood pressure is decreased below 90 mmHg and if there are accompanying symptoms, until the subject recovers from the symptoms. When resuming treatment, consider decreasing the dose. When hypertension cannot be controlled with the addition of new hypotensive drugs or with more intensive therapy, decrease the dose by one level. When grade 3 hypertension recurs despite decreasing the dose and hypotensive treatment, decrease the dose further by one level.
Grade 4 Life-threatening (e.g., malignant hypertension, temporary or constant neuropathy, and hypertensive crises).	Terminate the administration of the investigational drug.

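### Table 6.3.1.2 starts the Grade 3 lenvatinib hold on systolic pressure alone but ends it on diastolic pressure, so it permits resumption while systolic pressure is still Grade 3

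*Combined protocol and SAP*

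**What the plan says.** Table 6.3.1.2 grades hypertension and gives an action for each grade.

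- **Grade 2:** "Systolic blood pressure of 140–159 mmHg and/or diastolic blood pressure of 90–99 mmHg", or a symptomatic diastolic rise. Dosing continues unless there are symptoms. If there are, the instruction is to "withdraw treatment until the subject recovers from the symptoms, and diastolic blood pressure is restored to" less than 90 mmHg.
- **Grade 3, definition:** systolic of at least "160 mmHg and/or diastolic blood pressure of" at least 100 mmHg, or a third, treatment-based route: "pharmacotherapy of two or more types, and greater intensive therapy than before is needed".
- **Grade 3, action:** "Withdraw treatment until the diastolic blood pressure is decreased below 90 mmHg", and until any symptoms have resolved. On resuming, a lower dose is to be considered. If pressure cannot be controlled with added or stronger drugs, the dose drops one level. A further one-level drop follows "When grade 3 hypertension recurs despite decreasing the dose and hypotensive treatment".

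The text above the table says that "dose modification will be made at the discretion of the principal investigator (or subinvestigator) with reference to" the table, and it strongly recommends hypotensive treatment.

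Section 6.3.1.1 has the general rule for other Grade 3 lenvatinib toxicity: "Interrupt lenvatinib until resolved to tolerable Grade 2, or Grade 0-1". That section sends the management of hypertension to 6.3.1.2.

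**The concern.** The condition that starts the hold and the pressure condition that ends it use different measurements. Systolic pressure can start the hold by itself, but it plays no part in ending it. A patient held only because of systolic pressure can be released without any change in the value that caused the hold.

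Lenvatinib inhibits VEGFR, and the protocol treats hypertension as important enough to have its own dose rule. What is at stake is the soundness of that rule: it allows the drug to be restarted at a pressure that the same table calls Grade 3.

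**Working it through.** The protocol gives no figure to reproduce here. The check compares the entry and exit conditions of the Grade 3 row, then looks for a systolic limit anywhere else.

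**Inputs, all from Table 6.3.1.2** (SBP systolic, DBP diastolic, in mmHg)

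- Grade 3 entry, pressure part: SBP ≥ 160 or DBP ≥ 100.
- End of hold, pressure part: DBP < 90.
- End of hold, other part: symptoms resolved, if there were any.

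**Overlap.** A patient without symptoms is both Grade 3 and eligible to resume when (SBP ≥ 160 or DBP ≥ 100) and DBP < 90. DBP cannot be both ≥ 100 and < 90, so this reduces to SBP ≥ 160 and DBP < 90. The diastolic trigger is closed off properly; the systolic trigger is not.

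**Illustrative readings** (assumed, not from the documents; no symptoms, or symptoms resolved)

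| Reading | Grade 3 by pressure? | Resume condition met? | Systolic position |
|---|---|---|---|
| 175/85 | yes, 175 ≥ 160 | yes at once, 85 < 90 | 175 − 160 = 15, so a fall of more than 15 is needed to leave Grade 3 |
| 180/95 | yes, 180 ≥ 160 | no, 95 ≥ 90 | 180 − 160 = 20 above the boundary |
| then 172/88 | yes, 172 ≥ 160 | yes, after a diastolic fall of 95 − 88 = 7 | 172 − 160 = 12 above the boundary |

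At 175/85 the written hold has no minimum length, because it meets its own end condition when it starts.

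**Search for a systolic limit elsewhere**

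- Section 6.3.1.1: recovery to tolerable Grade 2 or lower would amount to SBP < 160 for a systolic trigger. But the section sends hypertension to 6.3.1.2 and does not say whether its own recovery rule still applies. The more natural reading is that the specific table governs.
- Section 4.2, exclusion criterion 4: mentions systolic 160 mmHg, but governs entry only.
- Opening of section 6: where following the protocol could be medically hazardous, the investigator is to change treatment on medical judgment. No pressure is given.
- Later steps of the Grade 3 row: these change the dose and set no systolic value for restarting.

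**With SBP < 160 added.** The hold ends only when SBP < 160 and DBP < 90. Neither pressure trigger (SBP ≥ 160 or DBP ≥ 100) can then be met at release, so the overlap is empty.

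**The case against.** The strongest reply is that nobody would apply the table mechanically. It is used at the investigator's discretion, and 6.3.1.1 also allows a hold or reduction beyond the listed conditions. The medical-hazard clause in section 6 is directive. A patient still at 172/88 continues to meet the Grade 3 definition, so the same row's instruction to hold can be said to apply again, and its reference to recurrence presupposes that Grade 3 has ended. Uncontrolled pressure also leads to a dose reduction.

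Much of this stands, and it limits the practical risk. It does not supply the missing limit. Discretion permits a longer hold without saying when it should end. If a reading both ends the hold and restarts it, the row is circular, and that needs correcting too.

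A reader might go further and infer that the limit must be 140 mmHg, because 140 and 90 are the lower ends of the two Grade 2 bands. The documents do not settle this. Asymptomatic patients at 140–159 mmHg continue dosing, and exclusion criterion 4 does not bar that range at entry. A limit of 140 could keep a patient off lenvatinib at the pressure at which that patient was enrolled. It is true that a patient who is Grade 3 by the treatment-based route at 150/85 would satisfy a limit of 160 at once, whereas a limit of 140 would need a fall of more than 10 mmHg (150 − 140). That patient's systolic pressure is not in the Grade 3 range, however, so the case lies outside this defect.

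**Conclusion.** The Grade 3 row is wrong as written, and a minor safety-rule correction is warranted. The rule permits resumption for any asymptomatic patient with systolic 160 mmHg or more and diastolic below 90 mmHg. This rests on the literal wording of the table and on reading the specific hypertension rule as governing over the general one in 6.3.1.1. If the general rule also applies, the two places conflict and the table still needs the same words.

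Three stronger readings are not supported. The protocol does not direct anyone to resume at Grade 3 systolic pressure; it only fails to prevent it. Nothing in the documents shows how often this would occur, so no count of affected patients can be given. And the point does not reach the objective response rate design: the 10- and 29-patient stages, the decision limits and the error rates do not depend on this table.

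**What to change.** In the Grade 3 row of Table 6.3.1.2, change the pressure condition to: *hold lenvatinib until systolic pressure is below 160 mmHg and diastolic pressure is below 90 mmHg*. Keep the symptom condition. Leave the Grade 2 row unchanged.

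A stricter systolic limit, such as below 140 mmHg, is a clinical option for the investigators, not a correction that the documents require.

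**Cost.** A few words in one table cell. Table 8.1 already lists systolic pressure among the vital signs, so no new data are needed, and eligibility, sample size and analysis do not change. Some patients will have longer lenvatinib holds, by an amount the documents do not give.

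The 28-day limits should be checked at the same time. Criterion 4 in section 6.2.1 requires both drugs to be off for more than 28 days, so a hold of lenvatinib alone does not meet it. The opening of section 6.3 is less clear. Its 28-day rule for late resumption names both drugs, then allows one to continue if the other is stopped. It could be read as needing both to be late or as applying to each drug separately. The intended reading should be confirmed, because under the second a long lenvatinib hold could end lenvatinib.

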6.3.2. Criteria for Changes in Pembrolizumab therapy

6.3.2.1 Dose modification of Pembrolizumab

For AEs (whether serious or non-serious) related to pembrolizumab exposure, immunological factors may be involved. Such AEs may occur immediately after the start of investigational drug administration or several months after the last dose. For toxicity and

severe or life-threatening AEs related to pembrolizumab, pembrolizumab therapy should be interrupted or discontinued in accordance with Table 6.3.2.1.

Table 6.3.2.1. Dose modification of Pembrolizumab

General instructions:			
Immune-related AEs	Toxicity grade or conditions (CTCAEv4.0)	Action taken to pembrolizumab	Monitor and follow-up
Pneumonitis	Grade 2	Withhold	
 Monitor participants for signs and symptoms of pneumonitis Evaluate participants with suspected pneumonitis with radiographic imaging and initiate corticosteroid treatment Add prophylactic antibiotics for opportunistic infections
	Grade 3 or 4, or recurrent grade 2	Permanently discontinue	
Diarrhea / colitis	Grade 2 or 3	Withhold	
 Monitor participants for signs and symptoms of enterocolitis (i.e. diarrhea, abdominal pain, blood or mucus in stool with or without fever) and of bowel perforation (i.e. peritoneal signs and ileus). Participants with \geq Grade 2 diarrhea suspecting colitis should consider GI consultation and performing endoscopy to rule out colitis.
	Grade 4	Permanently discontinue	

			
 Participants with diarrhea/colitis should be advised to drink liberal quantities of clear fluids. If sufficient oral fluid intake is not feasible, fluid and electrolytes should be substituted via IV infusion.
AST / ALT elevation or Increased Bilirubin	Grade 2	Withhold	
 Monitor with liver function tests (consider weekly or more frequently until liver enzyme value returned to baseline or is stable)
	Grade 3 or 4	Permanently discontinue	
Type 1 diabetes mellitus (T1DM) or Hyperglycemia	Newly onset T1DM or Grade 3 or 4 hyperglycemia associated with evidence of β -cell failure	Withhold	
 Monitor participants for hyperglycemia or other signs and symptoms of diabetes.
Hypophysitis	Grade 2	Withhold	
 Monitor for signs and symptoms of hypophysitis (including hypopituitarism and adrenal insufficiency)
	Grade 3 or 4	Withhold or permanently discontinue ¹	
Hyperthyroidism	Grade 2	Continue	
 Monitor for signs and symptoms of thyroid disorders.
	Grade 3 or 4	Withhold or Permanently discontinue ¹	
Hypothyroidism	No provision		
 Monitor for signs and symptoms of thyroid disorders.
Nephritis and renal dysfunction	Grade 2	Withhold	
 Monitor changes of renal function
	Grade 3 or 4	Permanently discontinue	

Myocarditis	Grade 1 or 2	Withhold	
 • Ensure adequate evaluation to confirm etiology or exclude other causes
	Grade 3 or 4	Permanently discontinue	
All Other immune-related AEs	intolerable/persistent Grade 2	Withhold	
 • Ensure adequate evaluation to confirm etiology or exclude other causes
	Grade 3	Withhold or discontinue based on the type of event. Events that require discontinuation include and not limited to: Guillain-Barre Syndrome, encephalitis	
	Grade 4 or recurrent Grade 3	Permanently discontinue	

1. Withhold or permanently discontinue pembrolizumab is at the discretion of the investigator or treating physician.
 
NOTE:
 
For participants with Grade 3 or 4 immune-related endocrinopathy where withhold of pembrolizumab is required, pembrolizumab may be resumed when AE resolves to ≤ Grade 2 and is controlled with hormonal replacement therapy or achieved metabolic control (in case of T1DM).
			

